Some studies have already been conducted in order to investigate the effects of different cleaning protocols for acrylic removable orthodontic appliances and may also help to reduce the risk of oral diseases related to biofilm growth, some different processes have been described such as denture cleaners, enzymatic solutions, chlorhexidine, sodium hypochlorite, or homemade solutions containing vinegar or citric acid (**Eichenauer *et al.*, 2011**). The two major approaches used for denture cleaning are mechanical and chemical methods. Mechanical methods include brushing (using water, soap, toothpaste, or abrasives) and ultrasonic treatment. Mechanical cleaning with brushes is inexpensive and common, but elderly and disabled patients might face difficulties with this method because of poor motor coordination, poor dexterity, and low motivation. There is evidence that mechanical cleaning with toothpastes can result in significant wear of conventional acrylic resins. Chemical method includes immersion of dentures in different cleansing solutions. Immersion in cleansing solution is an inexpensive, easy, and comfortable alternative procedure. Moreover, the cleansing solution can reach undercuts of the denture base that are difficult to clean mechanically, resulting in more efficient cleaning (**Schwindling *et al.*, 2014**).

No study is conducted to evaluate the most effective method used to remove biofilm from removable orthodontic appliance.

Research question:

What is the most effective method of cleaning an acrylic based removable orthodontic appliance?

Research hypothesis

The null hypothesis: There is no difference between the different methods of cleaning acrylic based removable orthodontic appliances.

Aims of the study:

The aims of the current study are:

1. To evaluate the effects of different cleaning regimes i.e. chemical and mechanical on biofilm formation of an acrylic based removable orthodontic appliance.
2. To find out if surface modification i.e. polished acrylic fitting surface, have an impact on cleaning the biofilm formation.

Methodology

Study design:

An in vivo study.

Setting:

It is double-blind, parallel, randomized clinical trial conducted in the orthodontic clinic after obtaining the ethical approval from the ethics committee of the department.

Subjects:

Orthodontic patient will be selected to wear a removable appliance for the study period.

Sample size:

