The acrylic tiles (5mm in diameter and 1mm thickness) will be placed and fixed into the holes, created by the metal discs, using sticky wax. The acrylic samples will be randomly seated as shown in figure 3.

The appliance will be sterilized using proper sterilization protocol.

Figure 3: The acrylic base containing the acrylic samples.

Method for biofilm detection

The removable appliance will be assigned randomly and blindly and fitted into the oral cavity of the patient for one week. Each individual will be given a pack containing the cleansing pack and an instruction sheet with a web link describing the cleaning regimen for his/ her appliance. The packs are similar in shape and color and will be prepared by a third person who does not know the purpose of the study. The volunteer will be grouped into three groups:

Group 1: patients will be instructed to brush both sides of the removable appliance once a day for 1 minute before bedtime using the toothbrush and the CHX toothpaste provided and water (**Albanna *et al.*, 2017**).

Group 2: patients will be instructed to immerse the appliance in 150 ml cup with tap water and dissolve one cleansing (**Albanna *et al.*, 2017**) tablet for 20 minutes according to the manufacture instructions.

Group 3: Combination of the chemical and mechanical methods first submitted to the mechanical method, followed by the chemical method (**Oliveira *et al.*, 2009**).

At the end of the study period, the acrylic samples will be removed carefully and applied into a petri dish containing PBS via a sterile tweezer. The samples will be then immersed twice in a 25ml sterile tubes containing

PBS to remove the planktonic bacteria and inserted into 5ml bijou tube containing 1mm PBS and 5 sterile glass beads. The sample will be vortex-mixed for 1 min to disseminate the biofilm and create a homogenous solution. Ten-fold serial dilutions will be carried out in PBS before the samples are plated onto blood agar (BA), to give the total anaerobic count, mitis salivarius agar (MS), a selective agar for streptococci and Mannitol salt agar (MA) for Staphylococci spp. BA and MS plates will be incubated anaerobically for 2-4 days at 37°C using anaerobic cabinet whereas the MA will be incubated for 2 days in aerobic condition. All organisms from both selective and nonselective agars will be distinguished by colony morphology and will be characterized by Gram reaction (**Al Groosh *et al.*, 2011**) and other confirmatory tests.

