Confirmatory test

1. Catalase testing: Catalase is a common enzyme found in nearly all living organisms exposed to oxygen (such as bacteria, plants, and animals) (**Chelikani *et al.*, 2004**). This test demonstrates the presence of catalase, an enzyme that catalysis the release of oxygen from hydrogen peroxide (H₂O₂). The catalase test is mainly used to differentiate between Gram-positive cocci: members of the genus Staphylococcus are catalase-positive, and members of the genera Streptococcus and Enterococcus are catalase-negative (**Whittenbury, 1964**).
2. Coagulase testing: Coagulase is a protein enzyme produced by several microorganisms that enables the conversion of fibrinogen to fibrin. In the research laboratory, it is used to differentiate between different types of Staphylococcus isolates. Importantly, *S. aureus* is generally coagulase-positive (**Ryan and Ray, 2004**).

Statistical analysis

All the data of the tested samples will be collected and analyzed using SPSS (statistical package of social sciences). In this study the following statistics will be used:

Descriptive statistics

- Mean.
- Standard deviation (SD).
- Minimum and maximum values.
- Statistical tables, figures and charts.

Normality test

Data distribution will be tested first using Shapiro-Wilk test to find that whether our collecting data are normally distributed or not.

Inferential statistics

- ANOVA (if the data parametric) or Kruskal Wallis test (if none parametric) to compare the effect of each cleaning agents on biofilm reduction of removable orthodontic appliance and Tukey HSD pot hoc test if there is significant difference between them.
- Independent t-test (if the data parametric) or Mann Whitney test (if none parametric) to compare the effect of each cleaning agents on biofilm reduction on polished and unpolished surface

In the statistical evaluation, the following levels of significance will be used:

Non-significant NS $P > 0.05$

Significant S $0.05 \geq P > 0.01$

Highly significant HS $P \leq 0.01$

Time table:

Duty	Expected time
Patient Identification and allocation	4 months
Intervention period	3 months
Data collection and analysis	2 months
Writing up the thesis	10 months (starting from the beginning of the study)
Total expected time to finish	About 10 to 11 months

Budget and Funding: The study is self-funded

Dissemination: Master Thesis.

References

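### Three culture counts share one null hypothesis and a 0.05 threshold, but none is primary; if each is tested, the chance of a false rejection is about 9–14%, not 5%

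*Combined protocol and SAP*

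**What the plan says.** The Research question asks for a single answer: which cleaning method works best. The Research hypothesis section states one null, "There is no difference between the different methods of cleaning acrylic based removable orthodontic appliances", and ties it to no outcome.

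The Method for biofilm detection section produces three outcomes. The media listed are blood agar "to give the total anaerobic count, mitis salivarius agar (MS), a selective agar for streptococci", and lastly mannitol salt agar for staphylococci. That makes a total anaerobic count, a streptococcal count and a staphylococcal count.

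The Inferential statistics list plans "ANOVA (if the data parametric) or Kruskal Wallis test (if none parametric) to compare the effect of each cleaning agents on biofilm reduction", followed by "Tukey HSD pot hoc test if there is significant difference between them". It does not say which count represents biofilm reduction. A separate line compares polished with unpolished surfaces.

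One threshold serves the whole section: "In the statistical evaluation, the following levels of significance will be used", with the first line "Non-significant NS $P > 0.05". The plan gives no primary outcome, no order of testing, no composite and no adjustment across counts. The Sample size section (13 per group) gives a citation but no outcome, so it does not imply a primary count either.

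**The concern.** One question with three candidate outcomes and no stated way to choose among them leaves the main conclusion open until the results are in. Two things follow.

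- **Error rate.** If the regimens are compared on each count at 0.05, the chance that at least one comparison is falsely significant exceeds 5%. The stated threshold then describes each test, not the trial's answer to its research question.
- **Decision rule.** Blood agar could favour one regimen and mannitol salt agar another. The plan does not say which would decide the most effective method, or whether a difference on one medium is enough to reject the null.

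Tukey HSD does not fill the gap. It protects the three pairwise regimen contrasts within one count, not the three counts.

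**Working it through.** **Inputs from the plan**
- Counts: 3 (Method for biofilm detection)
- Groups: 3, with 13 patients each, 39 in total (Method for biofilm detection; Sample size)
- Threshold: 0.05 for every test (Statistical analysis)
- Test: one-way ANOVA or Kruskal-Wallis. The ANOVA F statistic has 3 − 1 = 2 and 39 − 3 = 36 degrees of freedom.

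**Assumptions, because the documents are silent**
- Each count gets its own regimen test.
- One value per patient per count. The plan does not say how tiles are combined.
- Normal data with equal correlation between counts. No correlation is given, so a range of 0 to 0.9 is shown.

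**The plan's own figures.** The 13 per group cannot be re-derived, since no effect size, SD or power is given. The 0.05 can be checked: simulating a single count under the null gave rejection rates of 4.8–5.3%, as expected.

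**Independent counts.** P(at least one false rejection) = 1 − (1 − 0.05)³ = 1 − 0.857 = 0.143, or 14.3%.

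**Correlated counts.** Trials were simulated under the global null (60,000 per setting), and a false rejection was recorded if any of the three counts was significant:

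| Assumed correlation | ANOVA | Kruskal-Wallis | ANOVA plus a significant Tukey pair |
|---|---|---|---|
| 0 | 14.4% | 13.4% | 12.8% |
| 0.3 | 13.6% | 12.9% | 12.3% |
| 0.5 | 12.8% | 12.3% | 11.6% |
| 0.7 | 11.1% | 10.7% | 10.2% |
| 0.9 | 8.6% | 8.5% | about 8% |

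The ANOVA column is the chance of rejecting the null of no difference. The last column is closer to the chance of declaring one method better than another, since that also needs a significant pair.

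**After the change.** One primary count tested at 0.05 has a 5% error rate. If all three counts had to carry equal weight, Bonferroni at 0.05/3 = 0.0167 would give 1 − (1 − 0.0167)³ = 4.9% for independent counts, and at most 5% in any case.

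**The case against.** The strongest reply is that the plan never says each medium gets its own test, still less that one significant medium is enough. That is correct. A reader might infer a written any-of-three rule, but the Statistical analysis section speaks only of biofilm reduction. The defect is an unspecified outcome and decision rule, and the error rate is conditional on the natural reading. The point survives, because a single count chosen after the results are seen carries the same risk.

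A second reply is that the counts may be strongly correlated, since a total count can overlap with the selective ones. This also has force, and it is why the lower end of the range is about 9%. The rate approaches 5% only as the counts become nearly interchangeable.

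A third is that this is a self-funded Master's thesis and that open reporting of all three media is legitimate. It is. But the plan states a null hypothesis, asks for the most effective method and grades results by significance, so it should say which result answers the question.

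A reader might also add the surface comparisons (three media in three arms, nine tests) to the three regimen tests and quote 1 − 0.95¹² = 46%. The documents do not support that figure:
- Each appliance takes four tiles, randomly seated. The natural reading is that both surfaces sit in the same mouth, although the figure is not shown. The planned independent t-test is then conservative. With assumed within-patient correlations of 0.3–0.7 the twelve-test rate is about 12–30%, for between-count correlations of 0–0.7.
- The surface comparison belongs to Aim 2 and cannot reject a null about cleaning methods.
- The count of nine rests on one reading of an ambiguous line.

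**Conclusion.** The concern holds. The plan has three counts, one null and one threshold, with no primary outcome, no hierarchy and no adjustment across counts. If each count is tested at 0.05, the chance of at least one false omnibus rejection is about 9–14%, or about 8–13% when a significant Tukey pair is also required. These ranges assume one value per patient and between-count correlations from 0.9 down to 0. Separate testing is inferred, not written. Whatever the correlation, the plan has no rule for media that disagree. The trial can run as designed, but its stated 0.05 would not describe its main conclusion.

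**What to change.** Before any data are seen, add the following to the Statistical analysis section:

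- **Aim 1.** Name one count as the single primary outcome, with one value per patient, tested at 0.05. The blood-agar total anaerobic count is the natural candidate: it is the only non-selective measure, and the aims concern biofilm in general. The sponsor may choose another count if it is fixed in advance.
- **Other two counts.** Make them secondary, either Holm-adjusted across the two or reported with 95% confidence intervals and no significance claim.
- **Aim 2.** Treat it as a separate question with one overall polished-versus-unpolished test on the same count. Make the test paired within patient if each appliance carries both surfaces. Report surface results by arm and by medium descriptively.

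The cost is a few lines of text, with no extra patients or laboratory work, and the primary test keeps its full 0.05. The downside is that a significant result on a secondary count alone can no longer carry the main conclusion.

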C. Blood agar: is enriched medium used to culture those bacteria or microbes that do not grow easily. Such bacteria are called “fastidious” as they demand a special enriched nutritional environment as compared to the routine bacteria (**Sirois, 2020**).

Other materials:

- 1- Rubber bowl
- 2- Type IV stone
- 3- Gloves
- 4- Masks

5- Plastic petri dish

Procedure

Construction of acrylic samples with different surface texture:

Acrylic samples i.e. tiles of different surface texture will be made. An acrylic sheet of 1 mm thickness will be made using a mold with technique as shown in figure 3.

[figure not shown]

Figure 1: Acrylic samples made from polished and unpolished acrylic sheet.

A half of the sheet will be polished using a conventional polishing technique until a glossy surface appears, whereas, the remaining will be kept without modification. Tiles of 5mm in diameter will be bored using a trephine bur on both sides of the acrylic sheets and each set of tiles i.e. the polished and unpolished samples, will be color coated from its seated surface.

Construction of upper removable orthodontic appliance

An impression will be taken to the maxillary arch using alginate impression material (Hydrogum 5, Zhermack, Badia Polesine, Italy). The negative replica is then poured using type IV stone to make a study model. Four metal discs (5mm in diameter and 1.2mm thickness) will be placed on both sides of the palate as seen in figure 2; A.

[figure not shown]

Figure 2: Construction of the acrylic based orthodontic appliance. A, Study model with acrylic tiles; B, Fitting surface of the acrylic removable appliance.

The wire framework of the removable appliance will be fabricated using a 0.7 mm in diameter stainless steel wire (Spring hard, Dentarum, Ispringen, Germany) to make Adam's clasps on upper first premolars and molars to retain the appliance.

After applying a separating medium, an acrylic base will be fabricated using the orthodontic acrylic powder and liquid (Orthocryle, Dentaurum, Ispringen, German) with a ratio of (2.5 parts powder to 1 part liquid) according to the manufacturer's instruction. Before setting, a sprue or chimney like structure will be created through the acrylic dough to facilitate the metal discs and acrylic sample removal. The appliance then will be removed and the metal tiles will be dislodged using metal pin (Figure 2; B).

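### The unit of analysis and the pairing of surfaces are not stated: regimens go to patients, each appliance has four tile sites, and only tests for independent observations are planned

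*Combined protocol and SAP*

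**What the plan says.** **Allocation.** Under Method for biofilm detection, "The removable appliance will be assigned randomly and blindly and fitted into the oral cavity of the patient for one week", and "Each individual will be given a pack containing the cleansing pack and an instruction sheet" for that person's regimen. There are three regimen groups. The Sample size section counts thirteen patients per group.

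**Measurement.** Under Construction of acrylic samples with different surface texture, "Acrylic samples i.e. tiles of different surface texture will be made", so a sample is a tile. The appliance section places four metal discs on the palate, and tiles later fill the holes these leave. Of the layout the text says only that "The acrylic samples will be randomly seated as shown in figure 3". After a week the tiles are removed, rinsed and "inserted into 5ml bijou tube containing 1mm PBS and 5 sterile glass beads". The text moves between samples and sample here, so it is not clear whether each tile has its own tube.

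**Analysis.** "All the data of the tested samples will be collected and analyzed using SPSS". The regimen test is ANOVA or Kruskal-Wallis, "to compare the effect of each cleaning agents on biofilm reduction of removable orthodontic appliance". Surfaces are compared by "Independent t-test (if the data parametric) or Mann Whitney test (if none parametric"). The section names no unit of analysis, per-patient summary, patient term or paired test.

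**The concern.** Tiles in one appliance share a mouth, a week of wear and one person's cleaning, so their counts are likely to be correlated. The regimen is applied to the whole appliance. Only differences between patients therefore carry independent information about it.

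The ANOVA or Kruskal-Wallis test decides the study's null hypothesis of no difference between cleaning methods. If it is run on tiles, ordinary variation between patients could be read as a regimen effect. The surface comparison serves the second aim. If each patient carries both surfaces, an unpaired test discards the within-patient contrast that the design provides.

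**Working it through.** **Inputs from the documents.** 13 patients per group, 3 groups, 4 tile sites per appliance (read as four in total), significance level 0.05. The 13 rests on a citation, with no SD, effect size or power, so there is no calculation of the plan's own to reproduce.

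**Assumptions.** Two polished and two unpolished tiles per appliance; within-patient correlation ρ of 0.1 to 0.7; total SD within a surface of 1; surface difference δ of 0 to 2 SD; normal data; no regimen effect. The documents give none of these.

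**Step 1, counts.** 3 × 13 = 39 patients and 39 × 4 = 156 tiles. Error df are 3 × (13 − 1) = 36 on patients and 3 × (52 − 1) = 153 on tiles. The design effect is 1 + (4 − 1)ρ. At ρ = 0.3 it is 1.9, so the 52 tiles of a group are worth 52/1.9 ≈ 27 independent values.

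**Step 2, why the error can go either way.** For ANOVA on all tiles:

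- expected between-group mean square: 1 + 3ρ
- expected within-group mean square: [36(1 + 3ρ) + 117(1 − ρ)]/153 + 156(δ²/4)/153

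With 2 numerator df, P(F > x) = (1 + 2x/153)^(−76.5), which gives a 5% critical value of 3.055. Treating the within-group mean square as a scaled chi-square on 153 df is an approximation.

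- ρ = 0.3, δ = 0: between 1.9, within (68.4 + 81.9)/153 = 0.982. The effective cut-off is 3.055 × 0.982/1.9 = 1.58, and the true error is about 21%.
- ρ = 0.3, δ = 2: within 0.982 + 1.020 = 2.002. The cut-off is 3.055 × 2.002/1.9 = 3.22, and the true error is about 4.3%.

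Correlation raises the error. An unmodelled surface effect inflates the residual and lowers it.

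**Step 3, simulation of the regimen test (20,000 runs per setting), true error in %.**

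| Data entered in ANOVA | ρ = 0.1 | 0.3 | 0.5 | 0.7 |
|---|---|---|---|---|
| Four tiles pooled, no surface effect | 9.8 | 21.2 | 31.5 | 39.0 |
| Four tiles pooled, 1 SD | 5.7 | 14.1 | 22.3 | 30.8 |
| Four tiles pooled, 2 SD | 1.0 | 4.2 | 9.0 | 14.3 |
| Two tiles of one surface, analysed alone | 6.4 | 10.4 | 14.2 | 17.7 |

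Kruskal-Wallis on four pooled tiles gives 9.5 to 37.4% with no surface effect and 0.7 to 11.4% with 2 SD. If tiles of one surface share a tube and each surface is analysed alone, the error is about 5%. If they share a tube and surfaces are pooled, it is 7.8 to 20.1% with no surface effect and 0.1 to 2.5% with 2 SD. One mean per patient gives 4.6 to 5.2%.

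**Step 4, surface test within one regimen, both surfaces in each appliance.** With a patient effect only, true error in % and power for a 0.5 SD difference are:

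| Test | ρ = 0.1 | 0.3 | 0.5 | 0.7 |
|---|---|---|---|---|
| Independent t on tiles, error | 4.1 | 2.2 | 0.9 | 0.2 |
| Independent t on one value per surface, error | 3.1 | 1.0 | 0.3 | 0.0 |
| Independent t on tiles, power | 42.5 | 41.9 | 41.2 | 40.7 |
| Paired t, power | 41.6 | 50.5 | 65.3 | 85.6 |

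The paired test's error is 4.9 to 5.2%.

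Now let same-surface tiles in one mouth be more alike than tiles of different surfaces, by adding a patient-by-surface variance. For patient and patient-by-surface variances of 0.3 and 0, 0.3 and 0.2, 0.3 and 0.3, and 0.1 and 0.3, the error of the independent t-test on tiles is 2.0, 4.5, 5.4 and 7.9%. The paired test stays at 4.8 to 5.2%.

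**The case against.** The strongest reply is that the plan may intend one value per patient. The sentence on the data of the tested samples mainly names the software. The regimen bullet refers to the appliance, of which each patient has one, and the sample size is in patients. This stands to the extent that a reader might infer that the plan prescribes a tile-level analysis, and the text does not support that. What it supports is that the unit is left open, between about 36 and 153 error df. Patient-level summaries also would not cure the surface test: one polished and one unpolished value from the same patient are still paired data in an unpaired test.

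A second reply is that the size rests on quantities the documents do not give, and that some readings carry no error for the regimen test. That is right. A reader might infer that the regimen test must be anti-conservative; the 2 SD row and the shared-tube cases show otherwise.

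A third is that the tile layout may be plain in a figure not available here. So the layout cannot be called missing, and the pairing argument is conditional on it. The regimen argument needs only several tiles per patient, which the text states.

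**Conclusion.** The concern holds in conditional form and should be fixed before the counts are analysed. The plan names neither the unit of analysis nor any pairing. If tiles are entered as separate values, the regimen test's type I error is not controlled. With one value per tile and four tiles pooled it is about 10 to 40% with no surface effect and about 1 to 14% with a 2 SD surface effect, at an assumed correlation of 0.1 to 0.7. It is about 5% with one value per patient, or if tiles of one surface share a tube and each surface is analysed alone.

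If both surfaces sit in each appliance, the unpaired surface test is too conservative on one value per surface. A reader might infer that it is always conservative on tiles as well. That follows only if same-surface tiles in one mouth are no more alike than tiles of different surfaces; otherwise the error can exceed 5%. In these simulations the paired test stays near 5%. It gains power when patient-level correlation is moderate or high and patient-by-surface variation is small; at a correlation of 0.1 there is no gain.

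Confidence is medium, because the correlation, surface effect, tube handling and layout are all assumed.

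**What to change.** Add to Statistical analysis:

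> The patient is the unit of analysis. For the regimen comparison each patient contributes one value per count: the mean of the polished-tile mean and the unpolished-tile mean, on the scale analysed. Normality checks, ANOVA or Kruskal-Wallis and post hoc tests use these values, and n is reported as patients. Within each regimen, polished and unpolished surfaces are compared by paired t-test or Wilcoxon signed-rank test on per-patient surface means, with normality checked on the differences.

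If a mixed model is preferred, fit it to per-patient surface means with a patient intercept, or to tiles with both a patient and a patient-by-surface random term. A patient intercept alone on tiles is not sufficient. In a simulation with 39 patients and patient and patient-by-surface variances of 0.3 and 0.2, it gave 10.0% error for surface and 11.9% for the interaction; at 0.3 and 0.3 it gave 12.9% and 17.0%.

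If each appliance carries one surface only, compare surfaces between patients with one value per patient. A sentence on whether each tile has its own tube, and on the layout if the figure does not already settle it, would remove the remaining doubt.

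**Cost.** A few sentences, with no extra patients or laboratory work. The regimen test has about 36 error df (all 39 patients analysed) instead of up to 153, and its p-values will usually be larger but valid. Patients with one surface missing drop out of the per-patient mean unless a mixed model is used.

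### The listed numerical summaries (mean, SD, minimum, maximum) do not change when rank tests are used, and the count scale is unstated, so estimate and test may not match

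*Combined protocol and SAP*

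**What the plan says.** Under Statistical analysis, Descriptive statistics, four items are listed: the mean, the SD, "Minimum and maximum values", and "Statistical tables, figures and charts". The last names no summary measure.

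A Shapiro-Wilk test then selects the inferential method. For the regimens it is ANOVA or "Kruskal Wallis test (if none parametric) to compare the effect of each cleaning agents on biofilm reduction". For polished against unpolished surfaces it is a t-test or Mann-Whitney. The descriptive list has no corresponding switch.

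The outcome comes from plate counts: under Method for biofilm detection, "Ten-fold serial dilutions will be carried out in PBS" before plating on three media. No section says whether counts enter the analysis raw or log-transformed. No median, IQR, geometric mean, confidence interval or between-regimen difference is named anywhere.

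The Research question is "What is the most effective method of cleaning an acrylic based removable orthodontic appliance". The Sample size section gives thirteen patients per group, and there are three groups.

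**The concern.** The research question asks for an ordering of regimens and, implicitly, the size of the differences. A Kruskal-Wallis p-value gives neither, so the reader will turn to the tabulated summary. On the rank branch the plan offers an arithmetic mean and SD.

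Counts that need ten-fold serial dilution can span orders of magnitude. On the raw scale the mean of 13 such values depends largely on the one or two highest, and the SD says little about where most patients lie. The test compares ranks while the reported location follows the upper tail, and the two can point to different regimens. At stake are the reported effect size and ordering, not the validity of the test.

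**Working it through.** **Inputs.** From the documents: three groups, 13 patients per group, significance at P of 0.05 or below, and the listed summaries. The documents give no SD for the counts, so the log10 SD (s) is an assumption, shown at 0.5, 0.75 and 1. The plan gives no figure of its own on this point to reproduce.

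**Step 1: can mean and rank conflict?** Take regimen A with 12 patients at 10^4 and one at 10^7, and regimen B with 13 patients at 10^5.
- Mean of A = (12 × 10,000 + 10,000,000) / 13 = 10,120,000 / 13 ≈ 778,000. Mean of B = 100,000. By the mean, A looks almost eight times worse.
- Median of A = 10,000. Median of B = 100,000.
- Geometric mean of A = 10^((12 × 4 + 7)/13) = 10^4.23 ≈ 17,000, against 100,000 for B.
- Mann-Whitney favours A: only A's single high value exceeds any B value, so U = 1 × 13 = 13 of 13 × 13 = 169 pairs, p ≈ 0.00004.

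This shows only that a conflict is possible. The next steps ask how often it arises.

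**Step 2: is the SD informative on raw counts?** For a lognormal variable, SD/mean = √(exp((s · ln 10)²) − 1).
- s = 0.5: √(exp(1.151²) − 1) ≈ 1.7
- s = 0.75: √(exp(1.727²) − 1) ≈ 4.3
- s = 1: √(exp(2.303²) − 1) ≈ 14

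In simulated arms of 13 the sample SD exceeds the sample mean in about 61%, 93% and 98% of arms. The two highest patients carry a median 47%, 62% and 74% of an arm's total count.

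**Step 3: would the rank branch be reached?** In simulated trials on raw lognormal counts, Shapiro-Wilk applied arm by arm rejects normality in at least one arm in over 99% of trials, even at s = 0.5. If raw counts are analysed, the rank branch is therefore the expected one.

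**Step 4: how often do mean and rank disagree after a significant test?** 6,000 trials per setting, one value per patient, no zero counts, one arm truly lower by the stated gap. The table conditions on Kruskal-Wallis P of 0.05 or below.

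| s | Gap (log10) | Lowest-mean arm is not lowest-rank arm, among significant trials | Both significant and discordant, of all trials |
|---|---|---|---|
| 0.5 | 1.0 | about 0.1% | about 0.05% |
| 0.5 | 0.5 | about 1% | 0.9% |
| 0.75 | 1.0 | about 1.5% | 1.3% |
| 0.75 | 0.5 | about 7% | 2.3% |
| 1 | 1.0 | about 5% | 3.7% |
| 1 | 0.5 | about 13% | 2.8% |

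A repeat with a different random seed agreed closely (for example 12% and 5% at s = 1, and 6% and 1% at s = 0.75).

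**The case against.** A reader might infer that a few heavily colonised patients will often decide which regimen is declared best. In simulation with s = 1 and a 0.5 log10 gap, the truly best arm fails to have the lowest arithmetic mean in about 32% of all trials. The documents do not support that reading. The plan tests a null hypothesis and labels P above 0.05 non-significant, and in that setting Kruskal-Wallis is significant in only about 21% of trials. In the others the plan supports no regimen claim, whichever summary is tabulated. Part of the 32% is simply low power, since the geometric mean is also wrong in about 18%. The conditional figures in the table are the relevant ones, and they are much smaller.

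A reader might also infer that the plan commits to raw counts. It does not state a scale. If log10 CFU is intended, the listed mean is already the log of the geometric mean and most of the difficulty disappears. That objection stands, and it makes the unstated scale part of the point.

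The descriptive list is not worded as exclusive, and tables and charts could include medians. Nothing obliges them to, so this weakens the point without removing it.

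Finally, requiring the geometric mean as the headline would go further than the defect needs. The simulation has no zeros, which suits the geometric mean, whereas selective media may give zero counts after cleaning, and the result would then depend on the value substituted. That also stands, so the fix leaves the choice open.

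**Conclusion.** The point holds as a modest mismatch in reporting. The named summaries do not follow the test, and the analysis scale is not specified. If raw counts are summarised, the mean and SD are poor descriptions: the SD exceeds the mean in about 61% of arms at log10 SD 0.5, 93% at 0.75 and 98% at 1. The rank-test p-values are unaffected. A contradiction between the reported mean and a significant rank test is rare at log10 SD 0.5 (0.1-1%), uncommon at 0.75 (1.5-7%) and not negligible at 1 (5-13%), across gaps of 1.0 to 0.5 log10.

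These sizes rest on lognormal counts, an assumed log10 SD, one value per patient and no zeros. The absence of any between-regimen estimate or interval does not depend on those assumptions.

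**What to change.** State under Statistical analysis whether counts are analysed raw or as log10 CFU. Then, under Descriptive statistics, add the matching summary:

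- **Where a rank test is used:** median and IQR per group, with a Hodges-Lehmann shift and 95% CI for each pair compared.
- **If counts are analysed as log10 CFU:** mean log10 CFU (back-transformed, the geometric mean) and pairwise differences with 95% CI, with a convention for zero counts fixed in advance.

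Describe the most effective method from the summary that matches the test used, and keep the minimum and maximum as range only.

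The cost is a few lines of wording and some extra SPSS output, with no additional patients, visits or laboratory work. The one drawback applies on the log scale only: results depend on the zero-count convention, which the median does not need.
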